8.7. Hospitalization

Hospitalization is defined as any initial admission (even less than 24 hours) in a hospital or equivalent healthcare facility or any prolongation of an existing admission. Admission also includes transfer within the hospital to an acute/intensive care unit (eg, from the psychiatric wing to a medical floor, medical floor to a coronary care unit, or neurological floor to a tuberculosis unit). An emergency room visit does not necessarily constitute a hospitalization; however, the event leading to the emergency room visit should be assessed for medical importance.

Hospitalization does not include the following:

- Rehabilitation facilities;
- Hospice facilities;
- Respite care (eg, caregiver relief);
- Skilled nursing facilities;
- Nursing homes;
- Same day surgeries (as outpatient/same day/ambulatory procedures).

Hospitalization or prolongation of hospitalization in the absence of a precipitating, clinical AE is not in itself a serious adverse event. Examples include:

- Admission for treatment of a preexisting condition not associated with the development of a new adverse event or with a worsening of the preexisting condition (eg, for work-up of persistent pre-treatment laboratory abnormality);
- Social admission (eg, subject has no place to sleep);

- Administrative admission (eg, for yearly physical examination);
- Protocol-specified admission during a study (eg, for a procedure required by the study protocol);
- Optional admission not associated with a precipitating clinical adverse event (eg, for elective cosmetic surgery);
- Hospitalization for observation without a medical adverse event;
- Pre-planned treatments or surgical procedures. These should be noted in the baseline documentation for the entire protocol and/or for the individual subject.

Diagnostic and therapeutic non-invasive and invasive procedures, such as surgery, should not be reported as AEs. However, the medical condition for which the procedure was performed should be reported if it meets the definition of an AE. For example, an acute appendicitis that begins during the AE reporting period should be reported as the AE, and the resulting appendectomy should be recorded as treatment of the adverse event.

8.8. Severity Assessment

If required on the adverse event CRFs, the investigator will use the adjectives MILD, MODERATE, or SEVERE to describe the maximum intensity of the adverse event. For purposes of consistency, these intensity grades are defined as follows:

MILD	Does not interfere with subject's usual function.
MODERATE	Interferes to some extent with subject's usual function.
SEVERE	Interferes significantly with subject's usual function.

Note the distinction between the severity and the seriousness of an AE. A severe event is not necessarily an SAE. For example, a headache may be severe (interferes significantly with subject's usual function) but would not be classified as serious unless it met one of the criteria for SAEs, listed above.

8.9. Causality Assessment

The investigator's assessment of causality must be provided for all AEs (serious and non-serious); the investigator must record the causal relationship in the CRF, as appropriate, and report such an assessment in accordance with the serious adverse event reporting requirements if applicable. An investigator's causality assessment is the determination of whether there exists a reasonable possibility that the investigational product caused or contributed to an AE; generally the facts (evidence) or arguments to suggest a causal relationship should be provided. If the investigator does not know whether or not the investigational product caused the event, then the event will be handled as "related to investigational product" for reporting purposes, as defined by the Sponsor (see the section on

8.14 Reporting Requirements). If the investigator's causality assessment is "unknown but not related to investigational product," this should be clearly documented on study records.

In addition, if the investigator determines that an SAE is associated with study procedures, the investigator must record this causal relationship in the source documents and CRF, as appropriate, and report such an assessment in accordance with the SAE reporting requirements, if applicable.

8.10. Exposure During Pregnancy

For both unapproved/unlicensed products and for marketed products, an exposure during pregnancy occurs if:

1. A female becomes, or is found to be, pregnant either while receiving or having been exposed (eg, because of treatment or environmental exposure) to the investigational product; or the female becomes, or is found to be pregnant after discontinuing and/or being exposed to the investigational product;
2. An example of environmental exposure would be a case involving direct contact with a Pfizer product in a pregnant woman (eg, a nurse reports that she is pregnant and has been exposed to chemotherapeutic products).
3. A male has been exposed (eg, because of treatment or environmental exposure) to the investigational product prior to or around the time of conception and/or is exposed during his partner's pregnancy.

If a study subject or study subject's partner becomes or is found to be pregnant during the study subject's treatment with the investigational product, the investigator must submit this information to the Pfizer Drug Safety Unit on a Serious Adverse Event (SAE) report form and an Exposure During Pregnancy (EDP) Supplemental Form, regardless of whether an SAE has occurred. In addition, the investigator must submit information regarding environmental exposure to a Pfizer product in a pregnant woman (eg, a subject reports that she is pregnant and has been exposed to a cytotoxic product by inhalation or spillage) using the EDP Supplemental Form. This must be done irrespective of whether an AE has occurred and within 24 hours of awareness of the exposure. The information submitted should include the anticipated date of delivery (see below for information related to termination of pregnancy).

Follow-up is conducted to obtain general information on the pregnancy and its outcome for all EDP reports with an unknown outcome. The investigator will follow the pregnancy until completion (or until pregnancy termination) and notify Pfizer of the outcome as a follow up to the initial EDP Supplemental Form. In the case of a live birth, the structural integrity of the neonate can be assessed at the time of birth. In the event of a termination, the reason(s) for termination should be specified and, if clinically possible, the structural integrity of the terminated fetus should be assessed by gross visual inspection (unless pre-procedure test findings are conclusive for a congenital anomaly and the findings are reported).

If the outcome of the pregnancy meets the criteria for an SAE (ie, ectopic pregnancy, spontaneous abortion, intrauterine fetal demise, neonatal death, or congenital anomaly [in a live born baby, a terminated fetus, an intrauterine fetal demise, or a neonatal death]), the investigator should follow the procedures for reporting SAEs.

Additional information about pregnancy outcomes that are reported as SAEs follows:

- Spontaneous abortion includes miscarriage and missed abortion;
- Neonatal deaths that occur within 1 month of birth should be reported, without regard to causality, as SAEs. In addition, infant deaths after 1 month should be reported as serious adverse events when the investigator assesses the infant death as related or possibly related to exposure to the investigational product.

Additional information regarding the exposure during pregnancy may be requested by the investigator. Further follow-up of birth outcomes will be handled on a case-by-case basis (eg, follow-up on preterm infants to identify developmental delays). In the case of paternal exposure, the investigator will provide the study subject with the Pregnant Partner Release of Information Form to deliver to his partner. The Investigator must document in the source documents that the subject was given the Pregnant Partner Release of Information Form to provide to his partner.

8.10.1. Additional Postnatal Follow-up

The Investigator will be asked to assist with collection of assessments of postnatal development as part of a separate protocol. Participation in that protocol is optional and will require that the subject review, agree and sign a separate informed consent document specific to that study, explaining the details of the post-partum follow-up for the subject and the newborn to participate in these assessments of postnatal development.

8.11. Occupational Exposure

An occupational exposure occurs when during the performance of job duties, a person (whether a healthcare professional or otherwise) gets in unplanned direct contact with the product, which may or may not lead to the occurrence of an adverse event.

An occupational exposure is reported to the drug safety unit within 24 hours of the investigator's awareness, using the SAE report form, regardless of whether there is an associated AE/SAE. Since the information does not pertain to a subject enrolled in the study, the information is not reported on a Case Report Form (CRF), however a copy of the completed SAE report form is maintained in the investigator site file.

8.12. Withdrawal Due to Adverse Events (See Also Section on Subject Withdrawal)

Withdrawal due to AE should be distinguished from withdrawal due to other causes, according to the definition of adverse event noted earlier, and recorded on the appropriate adverse event CRF page.

When a subject withdraws because of an SAE, the SAE must be reported in accordance with the reporting requirements defined below.

8.13. Eliciting Adverse Event Information

The investigator is to report all directly observed AEs and all AEs spontaneously reported by the study subject. In addition, each study subject will be questioned about AEs.

8.14. Reporting Requirements

Each AE is to be assessed to determine if it meets the criteria for SAEs. If an SAE occurs, expedited reporting will follow local and international regulations, as appropriate.

8.14.1. Serious Adverse Event Reporting Requirements

If an SAE occurs, Pfizer is to be notified within 24 hours of investigator awareness of the event.

In particular, if the SAE is fatal or life-threatening, notification to Pfizer must be made immediately, irrespective of the extent of available AE information. This timeframe also applies to additional new information (follow-up) on previously forwarded SAE reports as well as to the initial and follow-up reporting of exposure during pregnancy, exposure via breastfeeding and occupational exposure cases.

In the rare event that the investigator does not become aware of the occurrence of an SAE immediately (eg, if an outpatient study subject initially seeks treatment elsewhere), the investigator is to report the event within 24 hours after learning of it and document the time of his or her first awareness of the AE.

For all SAEs, the investigator is obligated to pursue and provide information to Pfizer in accordance with the timeframes for reporting specified above. In addition, an investigator may be requested by Pfizer to obtain specific additional follow-up information in an expedited fashion. This information collected for SAEs is more detailed than that captured on the AE CRF. In general, this will include a description of the AE in sufficient detail to allow for a complete medical assessment of the case and independent determination of possible causality. Information on other possible causes of the event, such as concomitant medications, vaccines, and/or illnesses must be provided. In the case of a subject death, a summary of available autopsy findings must be submitted as soon as possible to Pfizer or its designated representative.

8.14.2. Non-Serious Adverse Event Reporting Requirements

All AEs will be reported on the AE page(s) of the CRF. It should be noted that the form for collection of SAE information is not the same as the AE CRF. Where the same data are collected, the forms must be completed in a consistent manner. For example, the same AE term should be used on both forms. AEs should be reported using concise medical terminology on the CRFs as well as on the form for collection of SAE information.

8.14.3. Medical Device Complaint Reporting Requirements

All medical device complaints, regardless of whether the medical device complaint is associated with an AE, will be collected on the applicable pages within the CRF. This includes potential incidents or malfunctions associated with the use of a medical device product. An incident or malfunction is an event that might have led to death or serious deterioration in health, or if it occurred again might have led to death or serious deterioration in health.

Pfizer is to be notified of all medical device complaints within 24 hours of the investigator's awareness of the event.

Refer to the Pharmacy Manual for procedures for forwarding medical device complaints not associated with an SAE to Pfizer.

8.14.4. Sponsor's Reporting Requirements to Regulatory Authorities

Adverse event reporting, including suspected unexpected serious adverse reactions, will be carried out in accordance with applicable local regulations.

9. DATA ANALYSIS/STATISTICAL METHODS

Detailed methodology for summary and statistical analyses of the data collected in this study will be documented in a Statistical Analysis Plan, which will be maintained by the sponsor. This document may modify the plans outlined in the protocol; however, any major modifications of the primary endpoint definition and/or its analysis will also be reflected in a protocol amendment.

The efficacy and safety population will be the ITT population, defined as all randomized subjects who received SC investigational product (either tanezumab or matching placebo).

9.1. Sample Size Determination

In terms of the study feasibility and the safety evaluation described below, the total sample size will be approximately 200 subjects (170-220 subjects, approximately 66 subjects [56-73 subjects] per treatment group). However, it is acceptable to randomize more than 220 subjects from the safety perspective as described below because primary objective is to evaluate the long-term safety.

Japanese subjects are enrolled in two studies within the tanezumab CLBP program (A4091059 and this study). In ongoing A4091059 study (randomization was finished in June 2017), 129 Japanese subjects were randomized and appropriately 57 Japanese CLBP subjects are expected to be initially randomized to the tanezumab arm. Considering approximately 133 (113-146) subjects are expected to be randomized to the tanezumab arm in this study, the safety data will be collected from approximately 190 (170-203) Japanese CLBP subjects treated with tanezumab.

The primary objective of this study is the evaluation of long term safety. The number of subjects who complete this study is estimated as described below. Both these protocols

require subjects to meet the efficacy response criteria (defined as at least a 30% reduction in weekly average LBPI score at week 16 relative to Baseline and at least a 15% reduction in weekly average LBPI score from Baseline at any week from week 1 to week 15) at week 16 in order to continue in the study. The proportion of 30% responders at week 16 was approximately 60% in two OA phase 3 studies (A4091011, A4091014) and approximately 42% in one CLBP phase 3 study (A4091012). On the other hand, the proportion of subjects discontinuing after week 16 is assumed to be approximately 10% for OA and approximately 20% for CLBP based on the results of discontinuation for reasons other than insufficient clinical response in these studies.

Therefore, the proportion of subjects expected to complete this study was calculated as approximately 54% ($=100*0.6*0.9$) based on the two OA studies and approximately 34% ($=100*0.42*0.8$) based on the CLBP study, and the proportion of completers of this study is estimated to be between 34% and 54%. Table 6 shows the relationship between the proportion of completers and the number of subjects with one year exposure.

From Table 6, if the proportion of completers is at least 43% in the CLBP program, approaching 100 subjects are expected to be treated with tanezumab for a minimum of one year.

Table 6. The relationship between the proportion of completer and number of subjects with one year exposure

Proportion of completers	Tanezumab treated Japanese sample size with 1 year of treatment exposure	
	CLBP program total	A4091063 only
54 %	91-109	61-78
50 %	85-101	56-73
45 %	76-91	50-65
43 %	73-87	48-62
40 %	68-81	45-58
34 %	57-69	38-49

(randomized 170 subjects in this study – randomized 220 subjects in this study)

As described below, when approximately 200 (170-220) Japanese subjects are enrolled in this study, the adverse events related to abnormal peripheral sensation and decreased sympathetic function are expected to occur in several Japanese subjects, so neurological safety can be evaluated with high probability in Japanese subjects.

Adverse events related to abnormal peripheral sensation¹

The incidence of adverse events related to abnormal peripheral sensation was 8.6% in the tanezumab 5 mg group and 15.6% in 10 mg group of the phase II controlled study of

¹ Details are described in [section 7.3.9](#).

tanezumab conducted in CLBP subjects (A4091012). Also, the incidence was 15.6% in 10 mg group of the phase II uncontrolled study (A4091039). Assuming that the true incidence rate of these events in the subjects enrolled in A4091059 and this study is nearly equal (10% in tanezumab treated subjects), when 170 subjects are enrolled in this study (approximately 113 subjects will be treated with tanezumab), these adverse events are expected to occur in 7 to 15 subjects (6%-13%) in this study at a probability of $\geq 80\%$, and in 12 to 22 subjects (7%-13%) in combined A4091059 and this study (approximately 170 subjects will be treated with tanezumab) at a probability of $\geq 80\%$.

Adverse events related to decreased sympathetic function²

The incidence of adverse events related to decreased sympathetic function was 6.0% in the tanezumab 5 mg group and 5.1% in 10 mg group of the phase II controlled study of tanezumab conducted in CLBP subjects (A4091012). Also, the incidence was 4.1% in 10 mg group of the phase II uncontrolled study (A4091039). Assuming that the true incidence rate of these events in the subjects enrolled in A4091059 and this study is nearly equal (6% in tanezumab treated subjects), when 170 subjects are enrolled in this study, these adverse events are expected to occur in 4 to 10 subjects (4%-9%) in this study at a probability of $\geq 80\%$, and in 6 to 14 subjects (4%-8%) in combined A4091059 and this study at a probability of $\geq 80\%$.

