		
screening stage 2.
 
• Clarify that facet joint injections and nerve blocks are prohibited beginning 30 days prior to IPAP and through Week 64.• Correct the activity in telephone contacts at Weeks 68, 72 and 76.• Provide clarification of the intended follow-up for subjects with severe and persistent joint pain.
Original protocol	28 August 2015	N/A

Rationale for protocol amendment 2

Background

Although inclusion criterion #6 has been updated to expand the number of pre-study non-steroidal anti-inflammatory drug (NSAID) for chronic low back pain treatment regimens that are considered to be qualifying in the amendment 1 (version date: 2 August 2016), an expected effect of enhancement of patient enrolment has not been achieved. Considering study feasibility, number of subjects with 1-year exposure and capability of safety evaluation with the data from this study, the protocol was amended to revise the target sample size.

Amendment 2

Considering study feasibility, number of subjects with 1-year exposure and capability of safety evaluation with the data from this study, the target sample size was updated to approximately 200 (170-220) subjects. However, it is acceptable to randomize more than 220 subjects from the safety perspective because primary objective is to evaluate the long-term safety.

PROTOCOL SUMMARY

BACKGROUND

Tanezumab is a monoclonal antibody that binds to and inhibits the actions of nerve growth factor (NGF). The Nerve Growth Factor Inhibitor (NGFI) class may offer an important breakthrough in the treatment of chronic pain and is under clinical investigation for the treatment of pain associated with osteoarthritis or other chronic pain conditions.

The completed Phase 2 and Phase 3 studies conducted to date have demonstrated that tanezumab is efficacious and generally safe and well tolerated for the treatment of pain due to osteoarthritis and chronic low back pain (CLBP).

This study will investigate the long term safety and efficacy of a fixed dose of tanezumab 5 mg and 10 mg administered subcutaneously (SC) seven times at 8-week intervals. The primary objective of this study is to evaluate the long-term safety of tanezumab 5 mg and 10 mg administered SC every 8 weeks (7 administrations). In addition, the study will evaluate the long-term analgesic efficacy of tanezumab 5 mg and 10 mg SC administered every 8 weeks (7 administrations).

STUDY OBJECTIVES AND ENDPOINTS

Primary Objective:

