In terms of study feasibility and safety evaluation, the total sample size will be approximately 200 subjects (170-220 subjects, approximately 66 subjects [56-73 subjects] per treatment group). However, it is acceptable to randomize more than 220 subjects from the safety perspective as described below because primary objective is to evaluate the long-term safety.

Japanese CLBP subjects are enrolled in two studies (A4091059 and this study). In ongoing A4091059 study (randomization was finished in June 2017), 129 Japanese subjects were randomized and approximately 57 Japanese CLBP subjects are expected to be initially randomized to the tanezumab arm. Considering approximately 133 (113-146) subjects are expected to be randomized to the tanezumab arm in this study, the safety data will be collected from approximately 190 (170-203) Japanese CLBP subjects treated with tanezumab.

The proportion of subjects expected to complete this study was calculated as approximately 54% based on two OA phase 3 studies (A4091011, A4091014) and approximately 34% based on one CLBP phase 3 study (A4091012), and therefore the proportion of completers of this study is estimated to be between 34% and 54%. If the proportion of completers is at least 43% in CLBP program, approaching 100 subjects would be treated with tanezumab for a minimum of one year.

As described below, when approximately 200 (170-220) Japanese subjects are enrolled in this study, the adverse events related to abnormal peripheral sensation and decreased sympathetic function are expected to occur in several Japanese subjects, so neurological safety can be evaluated with high probability in Japanese subjects.

Assuming that the true incidence of adverse events related to abnormal peripheral sensation in CLBP subjects enrolled in A4091059 and this study is 10%, when 170 subjects are enrolled in this study (approximately 113 subjects will be treated with tanezumab), these adverse events are expected to occur in 7 to 15 subjects (6%-13%) in this study at a probability of $\geq 80\%$, and in 12 to 22 subjects (7%-13%) in combined A4091059 and this study (approximately 170 subjects will be treated with tanezumab) at a probability of $\geq 80\%$.

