3. STUDY DESIGN

Figure 5. Study Schematic

This is a randomized, double-blind, active-controlled, multicenter, parallel-group Phase 3 study of the safety and efficacy of tanezumab when administered by SC injection for up to 56 weeks in subjects with chronic low back pain. Subjects will be randomized to 1 of 3 treatment groups in a 1:1:1 ratio. Treatment groups will include:

1. Placebo SC matching tanezumab administered at an 8-week interval (total of 7 times) plus celecoxib 100 mg BID to be administered orally for 56 weeks.
2. Tanezumab 5 mg SC administered at an 8-week interval (total of 7 times) plus placebo matching celecoxib to be administered orally BID for 56 weeks.
3. Tanezumab 10 mg SC administered at an 8-week interval (total of 7 times) plus placebo matching celecoxib to be administered orally BID for 56 weeks.

The study is designed with a total duration (post-randomization) of up to 80 weeks and will consist of three periods: Screening (up to 37 days; includes a Washout Period and an Initial Pain Assessment Period [IPAP]), Double-blind Treatment (56 weeks) and Follow-up (24

weeks). The Screening Period (beginning up to 37 days prior to Randomization) includes a Washout Period (lasting 2-32 days), if required, and an IPAP (the 5 days prior to Randomization/Baseline).

Prior to entering the study, subjects must be experiencing some benefit (eg, analgesic effect) from their current stable dose regimen of oral therapy of NSAID (celecoxib 200 mg/day [100 mg BID], loxoprofen 120 to 180 mg/day or meloxicam 5 to 15 mg/day) treatment, be tolerating their NSAID regimen, be taking this medication regularly (defined as an average of at least 5 days per week) during the 30 day period prior to the Screening Visit.

At the Week 16 visit, subjects must have at least a 30% reduction in weekly average LBPI score relative to Baseline and at least a 15% reduction in weekly average LBPI score relative to Baseline at any week from Week 1 to Week 15 in order to continue investigational product. Subjects who do not meet these response criteria will be discontinued from the Treatment Period and enter the 24-week Early Termination Follow-up Period (See Section 6.9.1).

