6.5.2. Study Conduct and Subject Disposition

The following subject dispositions will be summarized.

- Summary of number of patients treated by treatment group.
- Summary table and listing of inclusion and exclusion criteria that are not met by subjects who were screened (but not randomized).
- Summary of time to discontinuation by treatment group and reason, and study week of discontinuation for the treatment period (Weeks 1-2, 3-4, 5-8, 9-12, 13-16, 17-24, 25-32, 33-40, 41-48, 49-56, $>$ 56, total) and for the safety follow-up period (Weeks 1-8, 9-16, 17-24, $>$ 24, total).
- A summary of discontinuation up to End of Treatment period, and up to End of Study period.

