6.5.3. Study Treatment Exposure

The following study treatment exposure will be summarized.

- Number of SC doses taken.
- Summary of oral study medication compliance. This is calculated for the interval from Baseline to the entire post-Baseline period up to Week 56 (or end of treatment visit). Compliance is calculated as number of tablets dispensed minus the number returned divided by the number of days in the interval multiplied by 100, to get a percentage compliance for each patient. The number and percentage of subjects in each category (\geq 50%, \geq 80% and \geq 100% compliance) will be shown.

In addition, summary of duration in treatment period and post-treatment follow-up period will be summarized. The number and percentage of patients with each duration category will also be shown. The duration categories are 1-2, 3-4, 5-8, 9-12, 13-16, 17-24, 25-32, 33-40,

41-48, 49-56, >56 for duration in treatment period and 1-8, 9-16, 17-24, >24 for duration in post-treatment follow-up period, respectively.

6.5.4. Concomitant Medications, Non-Drug Treatments and Drug Treatments Prior to Start of Study Treatment

The following concomitant medications and non-drug treatment will be summarized.

- Concomitant drug treatments during the treatment phase through week 64 or up to 16 weeks post the last SC dose will be summarized. Summary of concomitant medications for non-NSAID medication and drug treatments for CLBP, concomitant NSAID medications, concomitant analgesics not used for CLBP, and concomitant non-drug treatments will be shown separately.
- Concomitant drug treatments after 16 weeks post last SC dose will be summarized for analgesics and other treatment for CLBP.
- Number of days of non-study NSAID use per dosing interval (eg, Baseline to Week 8 and Week 8 to Week 16, up to Week 56) and for Week 56 to Week 64. This will show the number and percentage of subjects in a dosing interval who exceeded the limit of 10 days of NSAID use. If a dosing interval exists, the visits will be used to define the interval, otherwise calendar time will be used. A summary of average number of days of NSAID use will be displayed by each interval. Also, a summary of the overall number of days of NSAID use from Day 1 to Week 64 will be shown, as well as the number and percentage of subjects who exceeded the limit of 80 days of NSAID use during this interval.

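### Protocol 9.1 and the Summary say 43% completion brings one-year tanezumab exposure close to 100 subjects; Table 6, cited in support, gives 73-87 (about 82 at the target size)

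*Protocol*

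**What the plan says.** Amendment 2 reduced the target size. Its rationale gives three grounds: "Considering study feasibility, number of subjects with 1-year exposure and capability of safety evaluation with the data from this study". Section 9.1 then states that "the total sample size will be approximately 200 subjects (170-220 subjects, approximately 66 subjects [56-73 subjects] per treatment group"). Allocation is 1:1:1, so two thirds receive tanezumab, which section 9.1 puts at about 133 (113-146). From the companion study A4091059, "57 Japanese CLBP subjects are expected to be initially randomized to the tanezumab arm". The program total on tanezumab is therefore about 190 (170-203).

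Section 9.1 estimates completion at between 34% (from the CLBP study) and 54% (from two OA studies). Table 6 turns completion rates into one-year counts for 170 and 220 randomised. Section 9.1 draws its conclusion from that table: "if the proportion of completers is at least 43% in the CLBP program, approaching 100 subjects are expected to be treated with tanezumab" for a year or more. The Statistical Method part of the Protocol Summary says the same without the table: "If the proportion of completers is at least 43% in CLBP program, approaching 100 subjects would be treated with tanezumab".

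**The concern.** The sentence names Table 6 as its source and picks out the 43% row, but that row gives 73-87 for the CLBP program and 48-62 for this study alone. Neither is close to 100. A reader of section 9.1 can see the mismatch, because the table follows. A reader of the Summary cannot see it without doing the multiplication.

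Long-term safety is the primary objective, and the number with one year of exposure is a stated ground for the reduced sample size. Anyone judging whether the reduced trial yields enough long-term exposure would take 43% completion as sufficient when the plan's own calculation says otherwise. The error is in the favourable direction. The separate calculation in section 9.1 of expected neurological adverse-event counts does not depend on it.

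**Working it through.** **Inputs (Protocol 9.1).** 57 Japanese tanezumab subjects from A4091059; 113, 133 and 146 from this study at 170, 200 and 220 randomised; completion range 34%-54%.

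**Program totals on tanezumab.** 57 + 113 = 170; 57 + 133 = 190; 57 + 146 = 203.

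**Reproducing the plan's figures.** The completion bounds are 0.60 × 0.90 = 54% and 0.42 × 0.80 = 33.6%, stated as 34%. Each Table 6 entry is the completion proportion times the number on tanezumab, rounded down. For the 43% row:

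- Program: 0.43 × 170 = 73.1 and 0.43 × 203 = 87.3, tabulated as 73-87.
- This study alone: 0.43 × 113 = 48.6 and 0.43 × 146 = 62.8, tabulated as 48-62.

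All 24 entries of Table 6 reproduce this way, so the table is correct. At the target size, which it omits, 0.43 × 190 = 81.7.

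**Completion needed.** Divide the wanted count by the program total. The documents set no threshold for a number close to 100, so 90 is shown as a lenient reading (my assumption).

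| Randomised here | Tanezumab total | Expected at 43% | Short of 100 | Completion for 100 | Completion for 90 |
|---|---|---|---|---|---|
| 170 | 170 | 73.1 | 27 | 58.8% | 52.9% |
| 200 | 190 | 81.7 | 18 | 52.6% | 47.4% |
| 220 | 203 | 87.3 | 13 | 49.3% | 44.3% |

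Every entry in the last two columns exceeds 43%, and the 58.8% also exceeds the upper planning bound of 54%.

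**Size needed at 43%.** For an expected 100: 100/0.43 = 232.6 on tanezumab; less 57 leaves 175.6 here; times 3/2 gives 263.3, so 264 randomised, 44 above the top of the planned range. For an expected 90: (90/0.43 − 57) × 3/2 = 228.5, so 229, which is also above 220.

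**At the CLBP-based rate.** 0.34 × 170 = 57.8 and 0.34 × 203 = 69.0, tabulated as 57-69.

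**Chance of reaching the figure.** Binomial, assuming independent subjects and one completion rate in both studies, for 170 / 200 / 220 randomised:

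- True completion 43%: at least 100 has probability below 0.01% / 0.5% / 4.2%; at least 90 has 0.6% / 12.7% / 37.6%.
- True completion 54%: at least 100 has probability 12% / 67% / 92%.

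**The case against.** The strongest reply is that no number in the plan is wrong. Table 6 is correct, the phrase is qualitative with no defined threshold, and the protocol sets no target of 100. The 43% is also stated as a floor: within the planning range it covers the rows up to 54%, and with 190 on tanezumab the expected count rises to 95 at 50% (0.50 × 190) and 102.6 at 54% (0.54 × 190). More than 220 may be randomised. The table sits beside the sentence in section 9.1, and the Summary gives the 190 (170-203) and the 34%-54%, so a reader could work out about 82. Nothing downstream inherits the statement: the SAP does not repeat it and no hypothesis is tested.

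Much of this is fair. The shortfall of 13-27 assumes that the phrase means 100; against 90 it is about 3, 8 and 17 at 220, 200 and 170. The probabilities are illustrative, because the sentence speaks of an expected number.

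It does not rescue the sentence. A floor presented as sufficient has to be sufficient, and at 43% the most favourable planned size gives 87. Exceeding 220 is allowed, but Table 6 stops there and 264 would be needed. That a reader of the Summary could find the discrepancy by multiplication is no reason to leave it.

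**Conclusion.** The concern holds. Table 6 is right and the sentence citing it overstates it, in section 9.1 and again in the Summary. At 43% completion the expected number with one year of tanezumab is 73, 82 or 87 at 170, 200 or 220 randomised. An expected 100 needs roughly 59%, 53% or 49% completion, and a lenient 90 still needs 53%, 47% or 44%.

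This rests on the protocol's own inputs: 57 tanezumab subjects from A4091059, two thirds of this study on tanezumab, one completion rate for both studies, and completers taken as the subjects with one year of exposure, as Table 6 does. It does not show that the sample size is wrong. It shows that one of its three stated grounds is described more favourably than the plan's arithmetic supports. It should be corrected.

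**What to change.** Restate the sentence in section 9.1 and in the Summary to agree with Table 6. For example: at 43% completion, 73-87 Japanese CLBP subjects (about 82 if 200 are randomised) are expected to have one year of tanezumab; about 53% completion at 200 randomised would be needed for 100; at the CLBP-based 34% the expected number is 57-69.

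An optional addition concerns reporting in this study only. SAP 6.5.3 groups treatment duration as "41-48, 49-56, >56 for duration in treatment period"; splitting the 49-56 week category at 52 weeks would count subjects with at least a year of treatment directly, by arm and for tanezumab combined. The sentence can be corrected without it, since Week 56 completers can already be derived from the disposition tables in SAP 6.5.2 ("A summary of discontinuation up to End of Treatment period, and up to End of Study period").

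The cost is one sentence in two protocol sections and a less favourable stated figure. No extra patients and no change of analysis are needed. The optional SAP split adds one category and, if tanezumab is to be shown combined, one pooled column.
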